#### 4.2 Exclusion Criteria

A subject who meets any of the following criteria will not qualify for the study.

1. Unwilling or unable to comply with the requirements of the protocol or are in a situation or condition that, in the opinion of an Investigator, may interfere with participation in the study (e.g., does not have reliable internet access).
2. History of allergy or sensitivity to naloxone, buprenorphine or other opioids, or history of any drug hypersensitivity or intolerance which, in the opinion of an Investigator, would compromise the safety of the subject.
3. Used an investigational drug within 30 days or 5 half-lives (whichever is greater) prior to randomization.
4. Received prescribed medication-assisted treatment with buprenorphine, methadone, or naltrexone for opioid use disorder within 14 days prior to screening.
5. Past or present diseases that, judged by an Investigator and based on available medical history/records, may jeopardize the safety of the subject or impact the validity of the study results.
6. Tongue piercing, or piercings in the mouth or oral deformities that may affect sublingual absorption, in the opinion of an Investigator.
7. Hospitalization for a psychiatric disorder in the past 30 days, not including inpatient treatment for drug rehabilitation.
8. Schizophrenia, or other serious mental illness defined as a mental, behavioral, or emotional disorder

resulting in serious functional impairment which substantially interferes with or limits participation in the study.

9. A Quick Inventory of Depression Symptoms - Self-Report (QIDS-SR, Appendix C) score  $\geq 16$  (severe depression) or a rating of 2 or 3 for question 12 (Thoughts of Death or Suicide) at screening.
10. A current diagnosis, other than opioid use disorder, requiring chronic opioid treatment.
11. Chronic pain that is unremitting or unstable.
12. Current DSM-V diagnosis of moderate to severe substance use disorder for psychoactive substances other than opioids, caffeine, marijuana, or nicotine.
13. Requires current use of medications that are strong inhibitors or inducers of cytochrome P450 (CYP) 3A4 (Section 4.3.1).
14. Any pending legal action that could affect participation or compliance in the trial.
15. Is an employee of the Investigator or the trial site, with direct involvement in the proposed trial or other trials under the direction of the Investigator or trial site, or is a family member of the Investigator or an employee.

#### 4.3 Restrictions

##### 4.3.1 *Concomitant Medication*

The following medications are prohibited during the study:

- CYP3A4 inhibitors - macrolide antibiotics (e.g., erythromycin), azole-antifungal agents (e.g. ketoconazole); the non-nucleoside reverse transcriptase inhibitor antiretroviral delavirdine; the protease inhibitor antiretrovirals atazanavir and ritonavir
- CYP3A4 inducers - rifampin, carbamazepine, phenytoin; the non-nucleoside reverse transcriptase inhibitor antiretrovirals efavirenz, nevirapine, and etravirine
- Monoamine oxidase inhibitors

#### 4.4 Withdrawal of Subjects

Every subject has the right to refuse participation in the study at any time and for any reason. A subject's participation must therefore be terminated immediately upon his/her request.

An Investigator or the sponsor may withdraw a subject from the study to protect the health of a subject. A subject will be withdrawn from the study for the following safety-related reasons:

- Subject experiences a serious adverse event (SAE) assessed as related to the study treatment by an Investigator or Orexo.

- Subject experiences other unacceptable AE(s) assessed as related to the study treatment by an Investigator.
- Subject requires a prohibited concomitant medication.
- Subject displays hypersensitivity reactions to BUP/NAL.
- Other significant subject safety issue as assessed by an Investigator or Orexo.

An Investigator will make every attempt to explain the reason(s) for discontinuation and to document this in the appropriate sections of the case report forms (CRFs) and in the source documentation, using the following as a guide:

- Subject requests discontinuation.
- Subject is non-compliant, defined as refusal or inability to adhere to the study procedures.
- Treatment failure, as defined by an Investigator, using any and all information including subject interview.
- Unacceptable or intolerable treatment-related AEs.
- Any illness or circumstance that would adversely affect the study procedures or outcome measures.
- At the request of Orexo, regulatory agencies, or institutional review board (IRB).
- Subject is lost to follow-up.

The final record will include reasons for withdrawal, AEs, and any necessary medical treatment.

Subjects who drop out of the study after randomization will not be replaced.

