3.3 Subject Data and Study Conduct

3.3.1 *Subject Disposition*

Counts and percentages of subjects who were randomized, discontinued early from the study, and completed the study will be summarized by treatment on all randomized subjects (FA Population). Reasons for early discontinuation will also be summarized.

For subjects that discontinued early from study, treatment success by treatment group will be investigated with a Kaplan-Meier survival plot, censored to when the subjects dropped out over the course of the study.

3.3.2 *Protocol Deviations*

Protocol deviations will be identified based on the clinical protocol as described in the Protocol Deviation Plan to align with ISO 14155:2020 (Clinical investigation of medical devices for human subjects – Good Clinical Practice). Protocol deviations will be identified prior to unblinding the database.

Counts and percentages of subjects with major protocol deviations by deviation category will be summarized by treatment based on FA Population.

3.3.3 *Analysis Populations*

Counts and percentages of subjects will be summarized by treatment based on FA Population.

3.3.4 *Demographic and Baseline Characteristics*

The following demographic and baseline characteristics will be summarized:

- Age (years)
- Sex
- Childbearing potential
- Race
- Ethnicity
- Baseline craving Visual Analog Scale (VAS)

Demographic and baseline characteristics will be summarized with descriptive statistics or counts and percentages of subjects as appropriate by treatment based on FA Population.

3.3.5 *Opioid Use History/ Treatment*

A treatment history, including counseling, over the previous 2 years for OUD will be recorded at screening. Opioid use history and treatment including main drug of abuse and primary route used, will be summarized by treatment based on Safety Population.

3.3.6 *Medical History*

Medical history will be coded to system organ class and preferred term using the Medical Dictionary for Regulatory Activities (MedDRA) version 24.0. Counts and percentages of subjects with medical history by system organ class and preferred term will be summarized by treatment based on the Safety Population.

3.3.7 *Concomitant Medications*

Concomitant medications that are ongoing on study Day 1 will be recorded. Additions, deletions, or changes to concomitant medications after Day 1 will not be recorded.

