3.4 Efficacy Assessment

Efficacy data will be summarized by randomized treatment based on the FA Population. The primary efficacy endpoint will also be summarized based on the mFA Population.

3.4.1 *Primary Endpoints Analysis*

The primary objective of the study is to determine whether the combination of SL BUP/NAL SOC background therapy and the digital therapeutic OXD01 is superior to SL BUP/NAL alone to reduce opioid use, as measured by the treatment success rate. Treatment success is defined as the subject having $\geq 80\%$ of urine drug tests negative for opioids plus $\geq 80\%$ of self-reports negative for illicit opioid use (from the TLFB interview at the same visit) from Week 6 to Week 25. Each subject will be evaluated as a success or failure for this metric and the proportion of subjects in each group demonstrating $\geq 80\%$ of urine drug tests negative for opioids plus negative self-reports for illicit opioid use (from the TLFB interview) will be tested using chi-squared test. Count and percentage of the subjects with treatment success will be summarized by treatment based on FA Population.

If the subject withdrew the study, then the urine drug tests for opioids and self-reports for illicit opioid use after withdrawal will be imputed as positive. If the subject completed the study with any missing visit, then the urine drug tests for opioids and self-reports for illicit opioid use for the missing visit will be imputed as positive.

Sensitivity analysis 1

As supportive analyses to the primary analysis for the primary endpoint, sub-group analysis using a similar chi-squared test as described above will be repeated for the following factors:

- Percentage of subjects meeting primary endpoint by reported compliance rate or who achieved greater than 80% completion of the visits during Week 6 to Week 25
- Subjects who took the dose of buprenorphine versus retention.
 - Target dose or lower: ≤ 16 mg buprenorphine for Suboxone or equivalent formulation; or ≤ 11.4 mg Zubsolv
 - Higher dose than target dose: > 16 mg buprenorphine for Suboxone or equivalent formulation; or > 11.4 mg Zubsolv
- Subjects who received additional behavioral health services

Sensitivity analysis 2

As supportive analyses, the primary endpoint and key secondary endpoints will be performed using the similar statistical methods based on mFA Population.

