2. Concomitant medications ongoing on Day 1 will be recorded.
3. As soon as the subject is clinically stable on SL BUP/NAL with physical withdrawal symptoms managed, and the subject able to fully participate in OXD01 training, but no greater than 14 days from the first dose of SL BUP/NAL induction.

Schedule of Events (Continuous): Weeks 13-25, Early Termination

| Evaluation | Treatment | | | | | | | Early Termination |
|--|-------------------|--------------------------------|--------------------|-----------------------------------|--------------------|----------------------------------|--------------------|-------------------|
| | Week 13 Day 85 | Week 14/15/16 Day 92/99/106 | Week 17 Day 113 | Week 18/19/20 Day 120/127/ 134 | Week 21 Day 141 | Week 22/23/24 Day 148/155/162 | Week 25 Day 169 | |
| Window | ± 1 Day | ± 1 Day | ± 1 Day | ± 1 Day | ± 1 Day | ± 1 Days | ± 1 Day | |
| Informed consent | | | | | | | | |
| Demographics | | | | | | | | |
| Inclusion/exclusion criteria review | | | | | | | | |
| Medical history | | | | | | | | |
| Opioid use history | | | | | | | | |
| Confirm diagnosis - OUD ¹ | | | | | | | | |
| Previous treatments for OUD | | | | | | | | |
| Concomitant medications ² | | | | | | | | |
| Physical examination | | | | | | | | |
| Vital signs | | | | | | | | |
| Urine drug screen | X | X | X | X | X | X | X | |
| QFI | | | | | | | X | X |
| TLFB interview – drugs and alcohol | | | | | | | X | X |
| TLFB interview – drugs | X | X | X | X | X | X | | |
| Review study restrictions with subject | X | | X | | X | | | |
| Randomization – IRS ³ | | | | | | | | |
| OXD01 – subject training ³ | | | | | | | | |
| Opioid craving VAS | X | | X | | X | | X | X |
| QIDS-SR | | | | | | | X | X |
| CGI-S | X | | | | | | X | X |
| CGI-I | X | | | | | | X | X |
| Review behavioral health therapies | X | | X | | X | | X | X |
| MAT compliance assessment/counseling | X | | X | | X | | X | X |
| OXD01 compliance assessment/counseling | X | | X | | X | | X | X |
| End of study interview | | | | | | | X | X |
| Adverse Events | X | X | X | X | X | X | X | X |

OUD – opioid use disorder; QFI – Quantity-Frequency Index; TLFB – timeline followback method; IRS – interactive response system; MAT – medication-assisted treatment; VAS – visual analog scale; QIDS-SR – Quick Inventory of Depression Symptoms, Self-Report; CGI-S/I – clinical global impression severity/improvement

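### Mandatory safety exits under protocol 4.4 end endpoint collection, the lost visits score positive, and no planned between-arm test varies that scoring: a cheap improvement

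*Protocol*

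**What the plan says.** **Exit rule.** Protocol 4.4 introduces its mandatory list with "A subject will be withdrawn from the study for the following safety-related reasons". The grounds are a treatment-related serious adverse event, another unacceptable related adverse event, need for a prohibited medicine ("Subject requires a prohibited concomitant medication"), hypersensitivity to BUP/NAL, and any other significant safety issue. Protocol 4.3.1 counts macrolide antibiotics and azole antifungals among the prohibited medicines. Section 4.4 gives no option to stop treatment and keep attending, and the schedule of events has no endpoint visits after early termination.

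**Scoring rule.** Under SAP 3.4.1, urine tests and self-reports "after withdrawal will be imputed as positive", whatever the reason for leaving. Visits missed by completers are also scored positive.

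**Planned supporting analyses.**
- SAP 3.4.1, sensitivity analysis 1, repeats the chi-squared test in subgroups. One is defined by compliance or by subjects "who achieved greater than 80% completion of the visits during Week 6 to Week 25".
- Sensitivity analysis 2 repeats the analyses "using the similar statistical methods based on mFA Population", which leaves out subjects at two sites for data reliability.
- SAP 3.3.1 plans a Kaplan-Meier plot of treatment success among early discontinuers, "censored to when the subjects dropped out over the course of the study". On discontinuation it adds: "Reasons for early discontinuation will also be summarized".

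**The concern.** Counting dropouts as opioid-positive is a common and defensible convention in this field, because leaving treatment often means relapse. That reasoning is weaker when the protocol itself orders the exit. Needing an antibiotic, for example, says nothing about opioid use and does not make a weekly urine test unsafe. An abstinent subject removed early on such a ground is recorded as a failure on values that nobody measured.

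Elsewhere the documents already separate stopping treatment from leaving the study. Protocol 7.4 lists withdrawal of the device as an action taken for an adverse event. Protocol 7.7 lets BUP/NAL stop in pregnancy without study exit. SAP 3.5.1 counts device discontinuation and study discontinuation separately.

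At stake is whether the primary result depends on the scoring of these subjects. The summary of discontinuation reasons by arm would show an imbalance, but nothing planned shows whether it changes the primary comparison.

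**Working it through.** **Inputs.** Visit weeks from protocol Figure 1; the 80% threshold from protocol 11.3 and SAP 3.4.1; 12% v 25%, 200 per arm and 90% power from protocol 11.6; two-sided 0.05 from SAP 3.1.5. The share of would-be successes lost to mandatory exits is not in the documents, so 2%, 5% and 10% are assumed.

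**1. The plan's own figure.** The normal-approximation formula is n = [1.96·√(2p̄q̄) + 1.2816·√(p₁q₁ + p₂q₂)]² / (p₂ − p₁)². With p̄ = 0.185 this is [1.96·√0.30155 + 1.2816·√0.2931]² / 0.0169, or 186 per arm, and 201 with continuity correction. Exact power at 200 per arm is 90.4% for Fisher's test and 92.6% for the uncorrected chi-squared test. The stated 200 per arm reproduces.

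**2. Visits and threshold.** Weeks 6 to 25 hold 7 evaluation visits (7, 9, 11, 13, 17, 21, 25) and 13 urine/self-report visits, 20 in all. Success needs 0.8 × 20 = 16 negatives, so 4 positives are allowed.

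| Last visit attended | Best possible score | Outcome |
|---|---|---|
| Week 20 or earlier | at most 15/20 = 75% | certain failure |
| Week 21 | 16/20 = 80% | success only if all 16 are negative |
| Week 22, 23, 24 | 17, 18, 19 of 20 | success possible |

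**3. Do the planned analyses vary the scoring?** More than 80% visit completion means at least 17 of 20. That subgroup drops anyone last seen at Week 21 or earlier (16/20 is exactly 80%). It keeps subjects last seen at Weeks 22, 23 and 24 with 3, 2 and 1 imputed positives. It selects on a post-randomization variable and re-scores nobody. The mFA analysis changes the subjects, not the scoring. The Kaplan-Meier plot does not count withdrawn subjects as positive, but it is descriptive, limited to early discontinuers and gives no alternative success-rate comparison.

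**4. Effect on power.** Let w be the share of would-be successes turned into failures. Success rates become 0.12(1 − w) and 0.25(1 − w), or 0.12 and 0.25(1 − w) if only OXD01 loses subjects. Power is the sum of the binomial probabilities of all outcomes with chi-squared of at least 3.84 at 200 per arm.

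| Assumed w | Both arms | OXD01 arm only |
|---|---|---|
| 0% | 92.6% | 92.6% |
| 2% | 92.0% | 90.8% |
| 5% | 91.0% | 87.6% |
| 10% | 89.2% | 80.4% |

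At w = 5% the expected losses are 0.05 × 24 = 1.2 control and 0.05 × 50 = 2.5 OXD01 successes.

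**5. Effect of re-scoring on the test** (uncorrected chi-squared, control v OXD01 successes of 200).

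| Counts | p |
|---|---|
| 24 v 50 (planned rates) | 0.0008 |
| 34 v 50 | 0.0495 |
| 35 v 50 (11 control subjects re-scored, no OXD01) | 0.067 |
| 35 v 61 (11 re-scored in each arm) | 0.002 |
| 24 v 39 (borderline) | 0.040 |
| 25 v 39 (one control subject re-scored) | 0.056 |
| 25 v 40 (one in each arm) | 0.042 |

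**The case against.** **The rule is a legitimate composite.** Treating a related serious adverse event or a hypersensitivity exit as failure is coherent. This stands, and it is why missing-as-positive should remain primary. It covers a newly needed macrolide or azole less well.

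**Such exits will be rare.** Protocol 4.2 excludes known drug sensitivity and current use of strong CYP3A4 inhibitors or inducers, and 8.1.1 expects few device events. This also stands and sets the weight of the point. The exclusion covers current need only, so a new need during 24 weeks still triggers exit.

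**The foreseeable bias is conservative.** Device-related exits can arise only in the OXD01 arm and count against it, so they do not create a false superiority claim. That is right. For the other grounds the direction is unknown. Several rest on unblinded judgement, but nothing in the documents points to an excess of control exits.

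**The result is not shown to be fragile.** A reader might infer from 35 v 50 that the trial hangs on this rule. The documents do not support that. The example re-scores 11 control subjects and none on OXD01, and equal re-scoring restores p = 0.002. If leavers would have succeeded at the planned 12% (an assumption), 11 such successes imply 11/0.12, or about 92 mandatory exits among 200 controls. One subject mattering at 24 v 39 is true of any threshold test.

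**Reasons are already recorded.** Protocol 4.4 requires reasons for withdrawal in the final record, and its guide has a catch-all entry. The remaining gap is narrow: the guide has no prohibited-medicine entry, so identifying the mandatory exits for analysis needs a coded field.

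**Conclusion.** The point holds as a cheap improvement. The protocol orders study exit on safety grounds, endpoint collection stops, the lost visits score positive, and no planned between-arm test uses another scoring.

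Two stronger readings do not hold. One is that every safety exit becomes a failure: subjects last seen at Weeks 21 to 24 can still meet the 80% threshold. The other is that nothing in the SAP departs from the positive rule: the Kaplan-Meier plot in SAP 3.3.1 does, though only descriptively.

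The expected effect is small: about two percentage points of power at an assumed 5% loss in both arms, and about five points if the loss falls on OXD01 alone. These figures rest on assumed loss shares and on the planned 12% and 25% not already counting such exits as failures. The documents do not settle that last condition.

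**What to change.** 1. **Protocol 4.4, for subjects still on study.** The listed reasons should lead to stopping or changing OXD01 or BUP/NAL as clinically needed. The subject then stays on the existing weekly urine and TLFB schedule to Week 25, unless consent is withdrawn, contact is lost or the visits themselves are unsafe. Score the observed results under the existing endpoint definition.

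2. **SAP 3.4.1.** Keep missing-as-positive as primary. Add one sensitivity analysis for subjects withdrawn on the mandatory 4.4 grounds: a tipping-point or best/worst-case count by arm, varied in both arms. Code the 4.4 ground on the CRF so that these subjects can be identified.

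**Left unchanged.** Scoring of prescribed replacement opioids should stay as it is. The endpoint requires urine tests negative for opioids, and the TLFB calendar has one drugs box per day, which cannot separate prescribed from illicit use. A urine screen at early termination is not worth adding for this purpose, since it gains at most one visit of 20.

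**Cost.** One short amendment, one CRF item and one analysis; the weekly visits are already scheduled. Sites must keep contacting subjects who are off treatment, some will refuse, and urine cannot be collected remotely (protocol 6.2). Visits that are still missed remain positive. Weeks already lost cannot be recovered, and SAP 3.2.2 shows that subjects had already been enrolled. For those subjects only the sensitivity analysis helps. It can still be added because the SAP is to be finalized before database lock (SAP 1), though it may rest on few subjects.

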#### **4.5 Safety Stopping Criteria for the Overall Study**

The clinical study will be stopped if the sponsor determines the safety risks for study subjects exceed the anticipated risks, as described in the study protocol. The following occurrences (non-exclusive) will trigger a re-evaluation of the risk assessment for the study, which could lead to a stop of the overall study:

- Occurrence of an unexpected SAE in the study assessed as related to OXD01 by an Investigator or sponsor (serious unanticipated adverse device effect as defined in Sections 7.1.3 and 7.1.4).
- Occurrences of SAEs, assessed as related to OXD01, at a higher rate or severity than expected as assessed by an Investigator or the sponsor.
- Occurrence of other significant subject risks in the study.

## 5. STUDY TREATMENT

### 5.1 Treatment Regimen

Eligible subjects will be randomized to one of two treatment groups in a 1:1 ratio:

- SL BUP/NAL SOC background therapy
- SL BUP/NAL + OXD01 digital therapy

Subjects in both groups will receive the assigned treatment for 24 weeks. Note: No investigational product will be administered as part of this study. Subjects in both groups may also be encouraged to participate in behavioral health therapies in accordance with the Investigator's standard of practice.

Prior to study Day 1 all subjects will have completed SL BUP/NAL induction, with physical withdrawal symptoms reduced so the subject is able to fully participate in OXD01 training, if randomized to that treatment group. Study Day 1 should occur as soon as the subject is clinically stable, with physical withdrawal symptoms managed and the subject able to fully participate in the process, but no greater than 14 days from the first dose of SL BUP/NAL induction.

Subjects randomized to SL BUP/NAL plus the OXD01 digital therapeutic will be trained to use OXD01 on Day 1 as directed in the OXD01 Clinician User Guide and will begin to access the therapeutic counseling modules for 15-30 minutes, 1-2 times per week as instructed.

### 5.2 Sublingual Buprenorphine/Naloxone Medication Assisted Treatment

The subject will obtain buprenorphine/naloxone sublingual tablets from a retail pharmacy with a prescription from the Investigator. Prior to study Day 1 subjects will initiate SL BUP/NAL, complete induction, and have physical withdrawal symptoms reduced so the subject is able to fully participate in OXD01 training, if randomized to that treatment group. Subjects will take the prescribed dose daily of SL BUP/NAL from Day 1 through Day 169 as directed by the Investigator.

